be programmed to obtain blood pressure recordings every 20 minutes for the daytime (awake) and every 30 minutes for the nighttime (asleep) for a 24-hour period. For the purposes of this study, daytime will be defined as 06:00-21:59 and nighttime will be defined as 22:00-05:59. Compliant 24-hour ABPM will be defined as a minimum of 14 successful daytime recordings and 5 nighttime readings. Those with less than these minimal thresholds will be asked to repeat the test. Should a non-compliant ABPM be unattainable, missing data will be handled with multiple imputation analysis. Normal ABP is defined as mean 24-hour BP <130/80 mmHg with a daytime (awake) BP of <135/80 mmHg and a nighttime (asleep) BP of <120/70 mmHg by ABPM according to guidelines.^{36,37} Average ABPM will be weighted for the proportion of daytime and nighttime blood pressure readings. At the time of data analysis, manual readings will be discarded when there is a concurrent automated reading within the same 5-minute period. In instances where the ABPM was recorded outside of the appropriate time (e.g., the participant did not follow instructions as to the timing of the test), each ABPM will be evaluated by two data analysts blinded to condition to determine

Flow-Mediated Dilatation analyses (FMD)

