As allopurinol is classified as FDA class C during pregnancy pregnant women will not be allowed in the study. Women with recent deliveries or third trimester pregnancy losses in the previous 3 months will be excluded because of unpredictable effects on FMD. A special question about the use of azathioprine will be included, since this can have a severe interaction with allopurinol.⁷⁸ Participants with serious medical conditions that in the investigator's judgment pose an unacceptable risk for exposure to a fixed dose of allopurinol (e.g. advanced heart failure, advanced liver disease or cirrhosis) will also be excluded.

H. Data collection and Statistical Analyses (see also Data Analysis plan)

Measures of central tendency (sample mean, sample media) and dispersion (sample variance, sample standard deviation) will be calculated for all outcome variables (e.g., hsCRP, endothelial function, and BP on ABPM) and covariates (e.g. age, race, etc.). For outcome variables, distributional properties will be evaluated using histograms and normal probability plots. When the assumption of normality is questionable, outcome

variable transformations will be examined to determine if the transformed variables approximate a normal distribution. will be transformed to achieve normality. Of the main study measures, we anticipate the distribution of hsCRP to be highly skewed. Consistent with prior studies, we will log transform hsCRP values for analysis. Possible outlying or inconsistent values will be detected and explored

Aim 1a: ULT and change in BP. The change in the average weighted 24-hour mean SBP and DBP will be compared among participants during the active treatment and placebo phases by paired t-test analysis.

Aim 1b: ULT and change in FMD. The change in the FMD will be compared among participants during the active treatment and placebo phases by paired t-test analysis.

Aim 1c: ULT and change in hsCRP. For each participant, we will first calculate the change in log transformed hsCRP from the beginning to the end of each crossover phase. The lack of an effect for the treatment sequence on the relative treatment responses will be confirmed using a treatment by sequence interaction term. Next, the within-participant change in hsCRP will be compared during the allopurinol treatment and placebo phases by paired t-test analysis.

Assessing differential treatment effects by race/ethnicity

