Comparison in the mean change achieved in the allopurinol treatment minus placebo phase between African Americans and other races/ethnicities will be performed initially using a t-test for independent samples. If differences are identified in the distribution of covariates, then the analysis will be completed with analysis of variance.

Assessing change in serum urate on change in hsCRP, FMD, and blood pressure

For this aim, the independent variable is change in serum urate and the outcome is change in hsCRP, FMD, and BP. First, participant factors associated with a significant change in serum urate will be identified using unadjusted age, race/ethnicity, and gender adjusted linear regression models. The correlation between change in serum urate with change in hsCRP, FMD, and SBP and DBP will be calculated using Spearman correlation coefficients. Using linear regression models, the association between changes in serum urate with changes in levels of each outcome, separately, will be determined. Models will include initial adjustment for age, gender, and race/ethnicity with subsequent models adjusted for other potential confounders (e.g. estimated glomerular filtration rate). In analyzing the association of change in serum urate on change in BP, we will additionally adjust for hsCRP and FMD, individually and together. The reduction in the association (i.e. beta coefficient) between change in serum urate and change in BP from before to after adjustment for these variables will provide insight into the degree that these mechanisms mediate the relation between ULT and BP reduction.

With 56 African Americans and 56 other races/ethnicities, we will be able to detect a difference in the increase of FMD of 1.48% for allopurinol versus placebo in African Americans compared to other participants.

The primary analyses will be on an intent-to-treat basis. All statistical analysis will be performed using SAS statistical software (SAS, Cary, NC) by analysts masked to randomization assignment. All study related information will be entered into a study database. This database will be maintained on a secure computer with access limited to study personnel only.

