As mentioned above, it is anticipated that the distribution for hsCRP will be skewed, and thus, we will log transform hsCRP. The sample size for the study is based on having 90% statistical power, assuming a two-tailed alpha error of 5% and a within person correlation of log transformed hsCRP between measurements of 10%. The intra-person standard deviation for log transformed hsCRP has been reported to be 0.52 log mg/L on serial measurements extending into a one year period.⁷⁹ To detect a difference in log transformed hsCRP of 0.25 (log mg/L) will require a sample size of 93 participants with complete hsCRP measurements (i.e., from baseline and closeout visits for each of the study phases). This is equivalent to a net reduction of hsCRP of 25% (e.g., from 2 mg/L to 1.5 mg/L or from 1 mg/L to 0.75 mg/L). This difference was chosen as it represents approximately half of one standard deviation in log-transformed hsCRP and is a meaningful decline to be observed over a four week period. Although we expect minimal loss to follow-up, we have taken the conservative step of increasing the sample size to account for 20% of participants not having complete data. Thus, we will recruit and randomize 112 participants for the proposed trial. For comparing differences in the net reduction in hsCRP for African Americans in comparison to other races/ethnicities, with 46 African Americans and 46 other races/ethnicities, we will have 90% statistical power to detect a differential reduction in log transformed hsCRP of 32 log mg/L (e.g., a 10 log mg/L reduction in whites and a 42 log mg/L reduction in African Americans).

Table 4. Statistical Power for Aim 2			
Proportion of Outcome Variance Explained by Control Variables	Incremental increases in R² due to the addition of change in serum urate in the presence of the control variables		
	.05	.075	.10
.10	.64	.82	.92
.20	.69	.87	.95
.30	.75	.91	.97

Power and sample size for aim 2

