This study will enroll women between the ages of 18-40 years, at which age we expect a greater majority to be fertile. If pregnancy occurs during the active treatment study period, there is a theoretical risk for the unborn as allopurinol is considered FDA class C during pregnancy. Untreated hypertension during the early pregnancy can also carry a small risk. Pregnant women will not be allowed in the study because allopurinol is classified as FDA class C during pregnancy, additionally prisoners, and institutionalized individuals will be excluded. Proper birth control methods for male and female participants will be confirmed and discussed during the screening visit.

8. Psychosocial risks

There are no obvious psychosocial risks

J. Potential Benefits

Currently, cardiovascular events caused by hypertension are the leading cause of morbidity and mortality in patients with gout and in the general population. If the addition of urate-lowering therapy to the standard therapy for hypertension reduces cardiovascular morbidity through improvement in endothelial function and inflammation in patients with hyperuricemia and those in the higher percentiles of normal serum urate concentration, this knowledge might have a significant impact on the quality of life of a large proportion of the general population.

K. Withdrawal of Participant Consent and Discontinuation of Study Drug

Participants can withdraw their consent at any time by informing the study coordinator.

This may include but is not limited to the following

- a. The subject deciding to withdraw consent for study
- b. An intolerable adverse event as judged by study investigator and/or participant
- c. The subject discontinuing acceptable birth control methods or becoming pregnant
- d. The subject enrolling in a conflicting investigational drug trial
- e. The participant BP > 160/110 between visit 2-5

If the study drug is discontinued, unless the subject withdraws consent, the subject will be followed for the full treatment period and all data will be collected as scheduled. Attempt will be made to schedule an early end of study assessment in the case of study drug discontinuation

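### Paired t-tests in Aims 1a–1c have no period term, and the hsCRP treatment-by-sequence check is the period contrast, so it cannot confirm that carryover is absent

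*Combined protocol and SAP*

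**What the plan says.** Section H gives one method for the three outcomes.

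- **Aim 1a (ambulatory BP):** the change in weighted "24-hour mean SBP and DBP will be compared among participants during the active treatment and placebo phases by paired t-test analysis".
- **Aim 1b (FMD):** "The change in the FMD will be compared among participants during the active treatment and placebo phases by paired t-test analysis".
- **Aim 1c (hsCRP):** "we will first calculate the change in log transformed hsCRP from the beginning to the end of each crossover phase". Then "The lack of an effect for the treatment sequence on the relative treatment responses will be confirmed using a treatment by sequence interaction term", and a paired t-test follows.

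No period term is named for any outcome. The sequence check applies to hsCRP only, and no action is stated if it is significant.

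On analysis sets and missing data, Section H also states: "The primary analyses will be on an intent-to-treat basis". Under Calculation of sample size, hsCRP is sized on "93 participants with complete hsCRP measurements (i.e., from baseline and closeout visits for each of the study phases". Section K says of a participant who stops study drug without withdrawing consent that "the subject will be followed for the full treatment period and all data will be collected as scheduled". The ABPM part of Section F adds: "Should a non-compliant ABPM be unattainable, missing data will be handled with multiple imputation analysis". No method is given for missing FMD or hsCRP.

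The case against carryover is made in Section F after Visit 3. It argues from drug half-life that thirty days of washout is enough, then reports that washout was later shortened to 2 weeks for men and some women.

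**The concern.** There are three linked problems.

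1. **No period term.** Treatment order is randomised, so phase is part of the design. A constant shift in level between phases cancels in change scores. A difference between phases in the mean change does not: it goes into the paired test's error variance, and it shifts the estimate if completers are unequal between sequences.

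2. **A check that cannot do its job.** If the treatment-by-sequence term is the same contrast as period, a significant result may only reflect a harmless period effect. A non-significant result does not rule out carryover that biases the treatment effect. Change scores give no protection, because residual drug effect at Visit 4 enters the phase 2 change directly.

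3. **Complete cases only.** A paired t-test needs both phases. For FMD and hsCRP this drops randomised participants despite the stated intent-to-treat basis.

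At stake is mainly the second point: a reassurance that carries no information on carryover, in a trial whose washout was shortened while it was running.

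**Working it through.** **Inputs from the documents.** SD 8.5 mmHg for SBP and 0.52 for log hsCRP; correlation 0.10; two-sided 5%; 93 complete, 112 randomised; effects 3.7 mmHg and 0.25 log. The documents give no period differences, carryover sizes or completer splits, so those below are assumptions.

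**The plan's own figures.** With SD of the treatment difference = SD × √(2(1 − 0.10)):
- SBP: 8.5 × √1.8 = 11.404 mmHg. At n = 93, power for 3.7 mmHg is 87.2%, not the stated 90%.
- log hsCRP: 0.52 × √1.8 = 0.698. The t-based sample size for 0.25 is 84. The stated 93 is obtained with zero correlation. At n = 93 and correlation 0.10, power is 92.8%.

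These discrepancies are a separate matter; 93 is used as given.

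**Aliasing.** Code the four sequence-by-period cells ±1. In the order AP phase 1, AP phase 2, PA phase 1, PA phase 2 (A = allopurinol, P = placebo), the treatment × sequence product is −1, +1, −1, +1. The period column is the same. Adding the product to intercept, sequence, period and treatment leaves the rank at 4.

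**What the check estimates.** Let π be the phase 1 minus phase 2 mean change under the same treatment. Let cX be the carryover of treatment X at Visit 5 minus its carryover at Visit 4. The expected A − P difference is:
- sequence AP: τ + π − cA
- sequence PA: τ − π + cP

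The check is their difference, 2π − (cA + cP). The bias in τ is (cP − cA)/2. These are different quantities.

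**hsCRP check, 47 v 46, true effect −0.25.** SE of the contrast = 0.698 × √(1/47 + 1/46) = 0.145.

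| Scenario | Check contrast | Check significant | Treatment estimate |
|---|---|---|---|
| π = 0.1, no carryover | 0.20 | 27.7% | −0.25 |
| π = 0.2, no carryover | 0.40 | 78.1% | −0.25 |
| Residual −0.10 at Visit 4, gone by Visit 5 (cA = +0.10) | −0.10 | 10.5% | −0.30 |
| Same residual, π = +0.05 | 0 | 5% | −0.30 |

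A simulation of 20,000 trials gave mean estimates of −0.249, −0.248, −0.301 and −0.300 for these rows.

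**Period term, SBP, n = 93, balanced sequences.** Paired-t variance = 11.404² + π² = 130.05 + π².

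| π (mmHg) | Variance ratio | Paired-t power | Period-adjusted power |
|---|---|---|---|
| 0 | 1.000 | 87.2% | 87.2% |
| 1 | 1.008 | 87.0% | 87.2% |
| 3 | 1.069 | 84.9% | 87.2% |
| 5 | 1.192 | 80.9% | 87.2% |

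**Unequal completers.** Bias = π × (n_AP − n_PA)/N. At 49:40 and π = 3 or 5: 3 × 9/89 = 0.30 and 5 × 9/89 = 0.51 mmHg. From 56:56 with random 20% dropout, the imbalance has SD √(2 × 56 × 0.8 × 0.2) = 4.2, and an imbalance of 9 or more has probability 4.4%. An imbalance of 4 gives 0.13 to 0.22 mmHg.

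**One-phase participants.** 112 − 93 = 19 (17%) fall outside the complete hsCRP cases. If all 19 have phase 1 only, adding them to a model with treatment, period and sequence multiplies the variance of the treatment effect by 0.924, 0.941 or 0.958 at a correlation of changes of 0.1, 0.3 or 0.5. That is a reduction of 4 to 8%.

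**The case against.** - **The plan does not mention carryover in this check.** True: it speaks of a sequence effect on treatment response, and its carryover argument is the washout. But the term cannot separate period from carryover under any label, and a non-significant test does not confirm absence.
- **Carryover of the assumed size is unlikely.** With the stated oxypurinol half-life of 18 to 30 hours, 14 days (336 hours) is at least 336/30 = 11.2 half-lives, leaving at most 0.04% of drug. The assumed −0.10 log is 40% of the target effect, and nothing in the documents suggests that size. The 5% row also needs a period effect chosen to cancel it. This stands as a reason to trust the washout. It does not make the check informative, and drug clearance is not the same as return of hsCRP, FMD or BP to baseline.
- **The paired test remains valid.** Sequences are balanced by stratified blocks, and random dropout gives imbalance with mean zero. At π = 3 mmHg with random 20% dropout, the type I error is about 4.4 to 4.6%. This stands: systematic bias needs dropout related to sequence.
- **The period effect may be smaller still.** If 8.5 mmHg is the SD of a single level and all four readings correlate at 0.10, the difference variance is 8.5² × 4 × 0.9 = 260. The inflation is then 0.4%, 3.5% or 9.6%. The placebo run-in may also dampen early drift.
- **The sample-size wording does not define the analysis set, and the 4 to 8% gain is a best case.** Both are fair, but a paired t-test still excludes anyone without both phases.
- **A period term may appear elsewhere.** Section H refers to a Data Analysis plan that cannot be identified in the supplied text. If it exists, Section H still has to agree with it.

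**Conclusion.** The concern holds. The firmest part is algebraic: the hsCRP check is the period contrast, so it can neither confirm absence of carryover nor attribute a positive result to it. Under the stated assumptions it flags a harmless period difference in 28% or 78% of trials. It misses a 20% overstatement of the effect in about 90% of trials.

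The missing period term is a modest loss. It costs almost nothing at 1 mmHg and about 6 points of SBP power at 5 mmHg; the bias is a few tenths of a mmHg when completers are uneven. For FMD and hsCRP, unused one-phase data are worth at most about 4 to 8% of the variance.

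Washout and the re-measured phase baselines remain the real protection against carryover. The change should be made but is not critical. Confidence is medium because of the unidentified Data Analysis plan.

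**What to change.** - For each outcome, fit one linear mixed model to the within-phase change: fixed effects for treatment, period, sequence, sex and race/ethnicity (the randomisation strata), and a random participant effect.
- Include every randomised participant with at least one evaluable phase, meaning a baseline and an end-of-phase value.
- Do not adjust for the Visit 4 baseline in the primary model, because phase 1 treatment can affect it.
- Delete the treatment-by-sequence term as confirmation of no sequence effect. Report Visit 4 against Visit 2 values of urate, hsCRP, FMD and ABPM by sequence, descriptively; these data are already collected.
- State that the period term does not remove carryover bias.
- State whether the ABPM imputation covers people who never enter phase 2.

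**Cost:** SAP wording and modest programming, with no new data. The model uses a few degrees of freedom; the period term alone uses one, about 0.01 percentage points of power at n = 93 if there is no period effect. It also relies on a missing-at-random assumption.

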In the context of a prospective, randomized study with crossover, **our specific aims are to:**

1. Determine in young adults with pre- or stage I hypertension whether ULT with 300 mg of allopurinol once daily over 4 weeks will:

1a. Lower blood pressure

Hypothesis 1: Four weeks of ULT therapy will induce a greater reduction in ambulatory blood pressure levels when compared to four weeks on placebo

Hypothesis 2: ULT will induce a greater reduction in ambulatory blood pressure levels in African Americans when compared with other races/ethnicities.

1b. Induce a change in endothelial function

Hypothesis 3: Four weeks of ULT will induce an improvement in endothelial function as indexed by flow-mediated arterial vasodilation (FMD) compared to placebo.

Hypothesis 4: ULT will induce a greater increase in FMD in African Americans when compared with other races/ethnicities.

1c. Induce a change in serum levels of high sensitivity C-reactive protein

Hypothesis 5: Four weeks of ULT will induce a greater reduction in serum levels of high sensitivity C-reactive protein (hsCRP) than placebo.

Hypothesis 6: ULT will induce a greater reduction in hsCRP in African Americans when compared with other races/ethnicities.

2. Determine if the impact of ULT on hsCRP, FMD, and blood pressure is associated with the change in serum urate achieved

Hypothesis 7: Changes in hsCRP, FMD, and blood pressure will be associated with the serum urate change observed after four weeks of ULT with allopurinol compared to placebo.

We initially aimed to recruit 112 young adults (ages 18-40 years) with pre-hypertension or JNC 7 stage I hypertension³⁷ not taking antihypertensive medication. Recruitment includes men, women, African Americans, and other races/ethnicities in equal numbers. To increase generalizability and add novelty to the research question, participants will not be required to be hyperuricemic, but to have serum urate levels ≥ 5.0

mg/dL for men and 4.0 mg/dL for women. Participants will be randomized to receive allopurinol or placebo in a four-week study with crossover. This novel translational study will generate knowledge about the mechanism by which ULT lowers blood pressure and provide evidence that can be translated into clinical practice for patients with gout or high-normal urate levels and other cardiovascular risk factors, including hypertension.

C. RESEARCH STRATEGY

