Women will need to be evaluated between days 1-7 of their menstrual cycles for study visits. This will be done to make FMD results comparable among women, and between women and men, since hormone levels have been shown to affect FMD results.⁷⁵ Participants will be entered into the trial and will be randomized to receive allopurinol or placebo. Neither the participant nor the Principal Investigator will know the drug assignment. This will begin Phase 1 (i.e., the first four weeks of the intervention). Randomization lists, stratified by race and gender, will be generated using a random number generator prior to the initiation of the study (i.e., in the first six months of study funding). Randomization will occur in blocks of size 2, 4, or 8 and will be stratified on sex and race/ethnicity to ensure order of treatment administration is balanced by sex and race. Randomization will occur using a random number generator. The sequence of treatment assignment will be determined by the random number generator and held by the pharmacist creating treatment arm study pill over-encapsulation. The pharmacist will maintain the master list and securely store the randomization files.

Visit 2:

- Blood pressure
- Updated medical history
- Blood sample
- Urine sample
- 24-hr ABPM
- FMD
- CBC
- Liver tests-Liver tests are alanine aminotransferase, aspartate aminotransferase, and alkaline phosphatase
- Serum creatinine
- Serum urate
- hsCRP
- Serum banking
- Pregnancy test†
- Cotinine test
- Pill count from run-in
- Potential adverse events
 - Assess any gastrointestinal symptoms, rash, or any other untoward effect
 - If potential untoward effect, study investigator will follow-up with subject

- Dispense 4 week course of allopurinol or placebo based on treatment assignment following return of the ABPM monitor

Interim visit check-in:

Between study visits, there will be four contact check-ins to encourage study compliance. These will be made by the study coordinator or research assistant. Additionally the study coordinator and/or research associate will assess the following during the call.

- Pill count
- Potential adverse events
 - Assess any gastrointestinal symptoms, rash, or any other untoward effect
 - If potential untoward effect, study investigator will follow-up with subject
 - If no untoward effects, subject will be encouraged to continue medication

Visit 3:

- Blood pressure
- Physical exam (head/neck/heart/abdomen)
- Updated medical history
- 24-hr ABPM
- FMD

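### The race comparisons (Hypotheses 2, 4 and 6) choose between an unadjusted t-test and ANOVA after looking at covariate balance; one prespecified ANCOVA would be cleaner and more powerful

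*Combined protocol and SAP*

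**What the plan says.** Section B (Specific Aims) states a race hypothesis for each Aim 1 outcome. Hypothesis 2 is "ULT will induce a greater reduction in ambulatory blood pressure levels in African Americans when compared with other races/ethnicities". Hypothesis 4 is "ULT will induce a greater increase in FMD in African Americans when compared with other races/ethnicities". Hypothesis 6 is "ULT will induce a greater reduction in hsCRP in African Americans when compared with other races/ethnicities".

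Section H, under the heading on differential treatment effects by race/ethnicity, gives the analysis for all three. The comparison of the mean allopurinol-minus-placebo change between the two groups "will be performed initially using a t-test for independent samples". The second step follows: "If differences are identified in the distribution of covariates, then the analysis will be completed with analysis of variance". The paragraph lists no covariates, does not say what counts as a difference, and writes down no model.

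Two other places bear on this. The next paragraph of Section H, on change in serum urate, specifies linear regression: "Models will include initial adjustment for age, gender, and race/ethnicity with subsequent models adjusted for other potential confounders". The Aim 2 power text then names five control variables (age, sex, race/ethnicity, body mass index, glomerular filtration rate). In Section F, randomisation "will be stratified on sex and race/ethnicity to ensure order of treatment administration is balanced by sex and race".

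The Section H heading also points to a data analysis plan. The combined document contains no further plan with an adjusted race model.

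**The concern.** Race is not randomised. Stratification balances treatment order within each race group; it does not make the groups alike in age, baseline urate, BMI or kidney function. The outcome is a within-person difference, so purely additive covariate effects cancel. A covariate distorts the race contrast only if it differs by race and also modifies the response to allopurinol. The protocol makes this plausible for urate. Section A.4 reports lower urate in young African Americans, and Hypothesis 7 expects response to follow urate change. The entry threshold for urate may narrow that gap.

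Three weaknesses follow for three of the seven hypotheses:

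- The model is picked after inspecting the data, by a rule with no stated threshold and no covariate list. Two analysts could reach different final analyses from the same dataset.
- If no imbalance is flagged, no covariate enters, and the precision from a prognostic covariate is given up.
- ANOVA in the strict sense takes categorical factors. A continuous covariate would have to be cut into groups, which leaves part of its influence in the race contrast.

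**Working it through.** **Step 1: the plan's own power figures.** Inputs from the sample-size section: 46 per group, 90% power, two-sided alpha 0.05, SD 8.5 mmHg for SBP and 6.3 mmHg for DBP. The detectable difference for an unadjusted two-group comparison is SD × √(2/n) × (1.960 + 1.282), with √(2/46) = 0.2085.

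- SBP: 8.5 × 0.2085 × 3.242 = 5.75 (5.81 with the t distribution). Stated: 5.8.
- DBP: 6.3 × 0.2085 × 3.242 = 4.26 (4.30 with the t distribution). Stated: 4.3.

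Both reproduce, so the blood pressure race power was computed with no covariate in the model.

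**Step 2: false positives when there is no race effect given the covariate.** The documents give no imbalance, no correlation and no trigger, so these are assumptions. The covariate mean differs between groups by d SD, the covariate correlates r with the treatment difference, and imbalance is flagged at p<0.05. If nothing is ever adjusted, the contrast is shifted by d × r SD, against a standard error of 0.2085 SD.

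- d = 0.3, r = 0.3: 0.09/0.2085 = 0.43, giving rejection of about 7%.
- d = 0.5, r = 0.5: 0.25/0.2085 = 1.20, giving rejection of about 22%.

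Simulation, 46 per group, 6,000 trials per row:

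| d | r | Imbalance flagged | t-test only (not the plan's rule) | Two-step, ANCOVA fallback | Always ANCOVA |
|---|---|---|---|---|---|
| 0.3 | 0.3 | 30.2% | 7.3% | 5.4% | 5.2% |
| 0.3 | 0.5 | 29.4% | 10.4% | 5.7% | 4.6% |
| 0.5 | 0.3 | 65.9% | 11.4% | 5.4% | 4.9% |
| 0.5 | 0.5 | 65.8% | 21.8% | 5.8% | 4.8% |

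If the fallback is a strict ANOVA with the covariate split at its median, the two-step rule rejects 5.0% to 8.3% over the same grid. At r = 0.1 even the t-test alone rejects only 5.1% to 5.7%. At d = 0 or r = 0 every method stays near 5%.

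The flag is weak where it is needed: at an imbalance of 0.3 SD it fires in about 30% of trials.

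**Step 3: precision.** Adjusting for a covariate with correlation r multiplies the residual SD by √(1 − r²): 0.954 at r = 0.3 and 0.866 at r = 0.5, a 13% reduction. Take a race difference of 0.55 SD (assumed; the plan's SBP figure is 5.8/8.5 = 0.68 SD) with the covariate balanced, so that the two-step rule nearly always stays with the t-test.

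- Unadjusted: 0.55/0.2085 = 2.64, power about 74-75%.
- Adjusted, r = 0.3: 0.55/0.954 = 0.577 SD; 0.577/0.2085 = 2.77, power about 78%.
- Adjusted, r = 0.5: 0.55/0.866 = 0.635 SD; 0.635/0.2085 = 3.05, power about 85%.

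The adjusted powers use the t distribution; the normal approximation gives about one point more.

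**The case against.** A reader might infer that confounding would pass as a race effect in up to about one trial in five, from the 7-22% rejection rates of the unadjusted t-test. The documents do not support that. Those rates describe never adjusting, and Section H does adjust, in some form, once an imbalance is seen. A one-way ANOVA on race would only repeat the t-test and do nothing about the imbalance that prompted it. The sentence makes sense only if covariates enter, either as factors or as a loosely worded ANCOVA. On either reading the excess is small, and it rests on assumed correlations that are large for effect modification of a within-person difference.

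Nor can a reader conclude that the plan excludes sex. No covariates are listed, strict ANOVA can take sex as a factor, and equal recruitment by sex and race is planned.

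Two further objections have force. First, the hypotheses as worded ask whether response differs between the groups, and the unadjusted contrast answers that. An adjusted coefficient answers a conditional question, and adjusting for baseline across non-randomised groups can change the answer as well as sharpen it. Second, BMI and baseline urate may lie on the pathway from race to response, so conditioning on them could remove part of the effect sought. Both narrow the remedy: the unadjusted contrast should stay, and those covariates belong in a sensitivity model. Neither justifies choosing the model from the data.

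Reading ANOVA as ANCOVA is possible, but the neighbouring Aim 2 paragraph says linear regression where regression is meant. Even on that reading the covariates and the trigger are unspecified.

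**Conclusion.** The point stands as a weakness in prespecification and efficiency, with a modest effect on error rates. Hypotheses 2, 4 and 6 have no fixed adjusted analysis anywhere in the supplied text. Under the assumptions above, the two-step rule costs about 0 to 1 percentage point of false-positive rate if the fallback is ANCOVA, and up to about 3 points if covariates are median-split. At a correlation of 0.1 there is almost no inflation. The more dependable gain from always adjusting is power: roughly 3 points at correlation 0.3 and 10 at correlation 0.5, for a 0.55 SD race difference with a balanced covariate. All these sizes depend on assumed imbalance, correlation, effect and trigger. That the model is chosen after looking at the data does not depend on them.

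**What to change.** In Section H, replace the conditional step with one prespecified linear model (ANCOVA) of each participant's allopurinol-minus-placebo change on race, sex, treatment sequence, the visit 2 baseline value of the outcome, and age. Fit it regardless of observed imbalance, for each Aim 1 outcome, and report the race coefficient with its 95% CI. Keep the unadjusted contrast beside it as the descriptive comparison. Add BMI, eGFR and baseline urate in a sensitivity model, and say why they are kept separate: BMI and urate may be on the pathway.

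The cost is a few sentences and no new data, since all these variables are already collected. With 92 complete participants, residual degrees of freedom fall from 92 − 2 = 90 to 92 − 6 = 86, and to 83 in the sensitivity model. The text should state that the adjusted coefficient is conditional and the unadjusted contrast marginal, so that a difference between the two is not read as an inconsistency.
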